QTcF	QT interval corrected with the Fridericia formula
PTB	Pulmonary tuberculosis
RR	Rifampicin resistant
SAE	Serious Adverse Event
SABA	short-acting beta agonist
SAP	Statistical Analysis Plan
SBP	Systolic Blood Pressure
SIFT-MS	Selected Ion Flow Tube Mass Spectrometry
SOC	System Organ Class
SpMet	Methaemoglobin saturation
t	Time
TASK	TASK Applied Science (Pty) Ltd
TB	Tuberculosis
tds	three times a day
TEAEs	Treatment-Emergent Adverse Events
TMF	Trial Master File
TTT	Time to Sputum Culture Positivity
ULN	Upper Limit of Normal
WHO	World Health Organization
WOCBP	Women of Child-Bearing Potential
WONCBP	Women of Non Child-Bearing Potential
XDR	Extensively Drug Resistant

EBA Definitions

EBA	An agent's ability to kill mycobacteria expectorated in sputum during the first weeks of treatment.
EBA CFU	Determination of EBA by quantification of viable mycobacteria as colony forming units (CFU) on a solid media culture.
EBA TTP	Determination of EBA by quantification of viable mycobacteria as time to culture positivity (TTP) in an automated liquid culture system.

1. Protocol Synopsis

1.1. Synopsis

Sponsor:	Thirty Respiratory Limited (30 Respiratory) [name]
Funder:	Thirty Respiratory Limited (30 Respiratory)
Study Drug:	RESP301
Protocol Number	RESP30X-EBA
Protocol Title:	A Phase 2 Study to Evaluate the Early Bactericidal Activity, Safety and Tolerability of Nebulised RESP301 in Adults with Newly Diagnosed, Rifampicin Susceptible Pulmonary Tuberculosis
Treatment Indication:	Rifampicin Susceptible Pulmonary Tuberculosis
Test Product, Dose and Mode of Administration:	
The Investigational Medicinal Product (IMP) will be supplied as RESP301 6 mL solution, packaged in two differing 3.0 mL vials:
 
Active vial: Sodium nitrite [REDACTED] mannitol [REDACTED] solutionDiluent vial: Citric acid [REDACTED] 
These precursor solutions are mixed at point of use for inhaled administration via nebulisation (NEB), resulting in the release of Nitric oxide (NO) throughout the respiratory system, from the upper airways to deep into the lungs.
 
Assuming a 100% conversion rate, theoretically [REDACTED] of NO is delivered. However due to intra- and inter-patient variations, the delivered dose is estimated to be ~40%-60% of this dose (section 3.2). Dosing is once daily (qd), twice daily (bd) or three times a day (tds) dependent on the study treatment arm, for 14 days.

Control Product Dose and Mode of Administration:	
The Control Product will be supplied as isoniazid 75 mg (H), rifampicin 150 mg (R), pyrazinamide 400 mg (Z), ethambutol 275 mg (E) (i.e., HRZE) combination tablets. Dosing is qd for fourteen days based on participants body weight rounded up to the nearest whole number:
 
38 to 54 kg: 3 tablets55 to 70 kg: 4 tablets71 kg and over: 5 tablets 
The participants' screening weight will be used to determine the HRZE dose and this dose will be administered for the duration of the study.

Primary Study Objectives: Activity	
Stage 1:
 
To determine the Early Bactericidal Activity (EBA) of tds dosing of inhaled RESP301 6 mL dosed via NEB over 14 days of treatment.
 
Stage 2:
 
To determine the EBA of inhaled RESP301 6 mL dosed via NEB administered qd, bd alone, or tds in combination with HRZE, over 14 days of treatment to optimise the dosing schedule.

Study Design:	The study is a single-centre, open-label, parallel arm, randomised clinical study in two sequential stages, with no stratification. The study

endpoints are laboratory based and the microbiology staff will be blinded to treatment allocation. A total of up to approximately 15 participants will be recruited per treatment arm (total of approximately 75 participants in the study). Control arm participants will be split across stage 1 and 2.

Stage 1: Treatment arms and participant numbers are described in Table 1.

Table 1: Stage 1 Treatment Arms

Treatment Arm	Treatment	Approximate Number of participants
1 (Active):	Inhaled RESP301 6mL via NEB tds	15
2 (Control):	HRZE po qd	5

HRZE: Isoniazid 75 mg /Rifampicin 150 mg /Pyrazinamide 400 mg /Ethambutol 275 mg, NEB: nebulisation, qd: once daily, po: per os/orally, tds: three times a day

On completion of Stage 1, recruitment will be paused and an interim analysis performed. Dependent on these results a Steering Committee will determine whether the study should proceed to Stage 2.

Stage 2: Treatment arms and participant numbers are described in Table 2.

Table 2: Stage 2 Treatment Arms

Treatment Arm	Treatment	Approximate Number of participants
2 (Control):	HRZE po qd	10
3 (Active):	Inhaled RESP301 6 mL via NEB qd	15
4 (Active):	Inhaled RESP301 6 mL via NEB bd	15
5 (Active):	Inhaled RESP301 6 mL via NEB tds plus HRZE* po qd	15

HRZE: Isoniazid 75 mg /Rifampicin 150 mg /Pyrazinamide 400 mg /Ethambutol 275 mg. NEB: nebulisation, bd: twice daily, po: per os/orally, qd: once daily, tds: three times a day

The per participant involvement in the study is illustrated in Figure 1.

	
Figure 1: Trial schematic
 
HRZE: Isoniazid 75 mg /Rifampicin 150 mg /Pyrazinamide 400 mg /Ethambutol 275 mg. NEB: nebulisation, bd: twice daily, po: per os/orally, qd: once daily, tds: three times a day

	
The participant will be admitted to the EBA unit during screening and discharged on day 16 of the study. During the treatment period daily study “visits” will occur where study assessments are performed, unless the participant is withdrawn early from the study. The follow-up visit will occur for all participants (completed treatment or early withdrawals).
 
On discharge from the EBA unit, participants will be referred to the local community TB clinics to continue standard anti-tuberculosis chemotherapy according to national guidelines. The participants will be provided with a referral letter and sufficient TB medication to cover the time from attending their last visit at the EBA unit until their scheduled visit at the TB clinic. This will be documented in the participants source documents.

Patient Population:	
A total of approximately 75 male and female participants, aged between 18 and 65, inclusive, with sputum positive newly diagnosed, rifampicin susceptible pulmonary tuberculosis (PTB), will be enrolled onto the study. Approximately 20 participants will be enrolled in Stage 1 and 55 participants enrolled in Stage 2. Participants who withdraw (section 4.4) may be replaced. Participants will be enrolled at the TASK centre in South Africa.

Eligibility Criteria	
Inclusion Criteria
 
Participants are required to meet all the following criteria to be randomized.
 
 Provide written, informed consent prior to all study-related procedures and agree to undergo all study procedures. Male or female, aged between 18 and 65 years, inclusive. Body weight (in light clothing and with no shoes) between 40 and 90 kg, inclusive. Newly diagnosed pulmonary TB. Either GeneXpert Mycobacterium tuberculosis (M.tb) positive with a quantitative readout of medium or high, OR acid-fast bacteria (AFB) sputum smear positive with a grade of at least 1+ on the IUATLD/WHO scale (Appendix 3:), on at least one pre-treatment sputum sample.

	
6. Rifampicin susceptible pulmonary TB as determined by molecular testing.7. Ability to produce an adequate volume of sputum as estimated from a pre-treatment overnight sputum collection sample (estimated 10 mL or more).8. A chest X-ray taken during the screening period or up to 2 weeks before screening which, in the opinion of the investigator, is consistent with pulmonary TB.9. Spirometry performed during screening with a Forced Expiration Volume in the first second (FEV1) of $\geq 40\%$.10. Be of non-childbearing potential or willing to use effective methods of contraception, as defined in section 4.3.4.
	
Exclusion Criteria
 
Participants will be excluded from participation if they fulfil any of the following criteria.

	
Medical History:
 
1. Evidence of clinically significant conditions or findings, other than TB, that might compromise safety or the interpretation of study endpoints, per discretion of the investigator.2. Clinical evidence of extra-thoracic TB, that might compromise safety or the interpretation of study endpoints, per discretion of the investigator.3. History of allergy to any of the study IMP as confirmed by the clinical judgement of the investigator.4. Alcohol or drug abuse, that in the opinion of the investigator, is sufficient to compromise the safety or cooperation of the participant.5. HIV positive AND:
(a) CD4 < 350 cells/mm³(b) OR are receiving antiviral therapy (ART).6. Methaemoglobin saturation (SpMet) $>3\%$.7. Female participant who is pregnant or breast-feeding.8. Participants planning to conceive a child within the anticipated period of study participation and for at least 90 days after the last dose of IMP in the study.
	
Treatment History
 
9. Participation in other clinical studies with investigational agents within 8 weeks prior to screening.10. Treatment received for this episode of TB with any drug active against M.tb [fluoroquinolones (including moxifloxacin, levofloxacin, ofloxacin and ciprofloxacin), bedaquiline, pretomanid, delamanid, ethionamide, isoniazid, ethambutol, amikacin, cycloserine, rifabutin, rifampicin, streptomycin,

	
kanamycin, pyrazinamide, para-aminosalicylic acid, rifapentine, thioacetazone, capreomycin, thioamides].
 
11. Treatment with immunosuppressive medications such as TNF-alpha inhibitors within 2 weeks prior to screening, or systemic corticosteroids for more than 7 days within 2 weeks prior to screening.
 
12. Treatment with nitric oxide and other nitric oxide donor agents (e.g., prilocaine, sodium nitroprusside and nitro-glycerine), phosphodiesterase inhibitors (e.g., sildenafil) and lung surfactant drugs (e.g., beractant, calfactant, poractant), within 30 days prior to screening.
 
Laboratory Safety Testing
 
13. Participants with the following toxicities at screening as defined by the enhanced Common Terminology Criteria for Adverse Events (CTCAE) toxicity table version 5.0, 27Nov2017 (
 
14. Appendix 1)
 
(a) creatinine >1.5 times upper limit of normal (ULN)(b) haemoglobin <8.0 g/dL(c) platelets <50x10⁹ cells/L(d) serum potassium <3.0 mmol/L(e) aspartate aminotransferase (AST) >3 x ULN(f) alanine aminotransferase (ALT) >3 x ULN(g) alkaline phosphatase (ALP) ≥ 2.5 x ULN(h) total bilirubin >1.5 x ULN(i) total white cell count <2 cells x 10⁹/L. 
NOTE: Investigations may be repeated once during screening if the initial result is unfavourable.

Study Duration	
Participants who complete the study will participate for a maximum of 37 days (screening period of up to 9 days, followed by a treatment period of 16 days and a follow-up visit at Day 28 from first dose of IMP).
 
The overall duration of participants involvement in the study is planned to be approximately 1.5 years (first participant in to last participant out, including the pause between stages 1 and 2 for the interim analyses and continuation decision).

Sample Size	
This is a proof-of-concept study without hypothesis testing. The planned sample size of 15 participants per treatment group is in keeping with other phase 2 studies of this type and accounts for the possibility of up to 3 dropouts per arm which represents a conservative estimate of the expected drop-out rate. Previous EBA studies indicate that a sample size of 12 participants per arm allowed for the identification of proof-of-concept i.e., change in TTP/CFU compared to no change in TTP/CFU for all evaluated arms.

1.2. Evaluations

	Objective	Outcome Variable/s	Statistical Analysis
Primary: Activity	
Stage 1 To determine the EBA of inhaled RESP301 6 mL tds dosed via NEB over 14 consecutive days.
 
Stage 2: To determine the EBA of inhaled RESP301 6 mL dosed via NEB administered qd, bd, or tds in combination with HRZE, over 14 days of treatment to optimise the dosing schedule.
	
Overnight sputum collection from which viable mycobacteria in the sample is quantified:
 
 as TTP using the Mycobacteria Growth Indicator Tube (MGIT) (Bactec™ MGIT™ 960) system. 
The samples from participants receiving HRZE alone serve to confirm that the laboratory assays result in the expected EBA for HRZE, thereby validating the method.
	
The EBA_{TTP} (0-14) in the MGIT (Bactec™ MGIT™ 960) system as determined by the predicted rate of change in the TTP in sputum over the period Days 0 to 14 will be analysed using linear, bi-linear, or non-linear functions using nonlinear mixed effects modelling of TTP over time.
 
Predicted estimates of rates of change including uncertainties for the potential differences in treatment effects between the study arms will be determined and graphically illustrated.

Secondary: Activity	
Stage 1 To determine the EBA of inhaled RESP301 6 mL tds dosed via NEB over 14 consecutive days.
 
Stage 2: To determine the EBA of inhaled RESP301 6 mL dosed via NEB administered qd, bd alone, or tds in combination with HRZE, over 14 days of treatment to optimise the dosing schedule.
	
Overnight sputum collection from which viable mycobacteria in the sample is quantified:
 
 as CFU on a solid media culture. 
The samples from participants receiving HRZE alone serve to confirm that the laboratory assays result in the expected EBA for HRZE, thereby validating the method.
	
The EBA_{CFU} (0-14) as determined by the predicted rate of change in log₁₀CFU per mL sputum over the period day 0 - 14 will be described using linear, bi-linear or non-linear functions using nonlinear mixed effects modelling as dictated by the data of log₁₀CFU over time and in relation to drug exposure.
 
Predicted estimates of rates of change including uncertainties for the potential differences in treatment effects between the study arms will be determined and graphically illustrated.

	Objective	Outcome Variable/s	Statistical Analysis
Secondary: Safety and tolerability	To determine the safety and tolerability of inhaled RESP301 6 mL via NEB administered qd, bd, and tds alone, or tds in combination with HRZE, over 14 days of treatment.	Measurement of: 
 • Adverse Events • Concomitant Medication • Safety Laboratory (Haematology, Chemistry, Urinalysis) • Methaemoglobin • Physical Examinations • Vital Signs • Body Mass Index (BMI). 	Incidence of Treatment Emergent Adverse Events (TEAEs) will be presented by severity, drug relatedness, seriousness, leading to early withdrawal and leading to death. Clinical laboratory measurements and vital signs will be summarized using descriptive statistics as actual values and changes from baseline. Physical examinations and concomitant medications will be listed.
Exploratory	To explore the EBA variability due to potential M.tb sterilisation in sputum samples as a result of NO contamination in sputum samples.	Overnight sputum collection from which viable mycobacteria in the sample is quantified as TTP using the MGIT (BactecTM MGIT™ 960) system.	Comparison of EBA _{TTP} (0-14) versus EBA _{TTP} (0-15) and the predicted EBA _{TTP} (14-15) versus observed EBA _{TTP} (14-15) analysed using linear and non-linear functions using mixed effects modelling of TTP over time and analysis of variance.

1.3. Study Flow Chart for Stages 1 and 2

Period	Screening			Treatment															FU 20 ^A	EWD	
	Visit 1	2	3	4	5	6	7	8	9	10	11	12	13	14	15	16	17	18	19		
Day (-9 to -3)	-2	-1	1	2	3	4	5	6	7	8	9	10	11	12	13	14	15	16	28		
Written Informed Consent	X																				
Demography	X																				
Medical & Treatment History	X																				
Physical Examination ^{B, C}	X			X	X	X	X	X	X	X	X	X	X	X	X	X	X	X	X	X	
Vital Signs ^C	X	X	X	X	X	X	X	X	X	X	X	X	X	X	X	X	X	X	X	X	
Height	X																				
IMP Administration ^D , and Compliance Check				X	X	X	X	X	X	X	X	X	X	X	X	X	X	X	X		
Concomitant Medication ^E	X	X	X	X	X	X	X	X	X	X	X	X	X	X	X	X	X	X	X	X	
Adverse Events ^F				X	X	X	X	X	X	X	X	X	X	X	X	X	X	X	X	X	
Eligibility Assessment ^G		X																			
EBA unit inpatient	X ^H	X	X	X	X	X	X	X	X	X	X	X	X	X	X	X	X	X	X ^I		
Randomisation ^J		X																			
Chest X-ray		X																			
Spot or Overnight Sputum ^{K, L}	X																				
Overnight Sputum ^{K, M}		X	X	X	X	X	X	X	X	X	X	X	X	X	X	X	X	X			
Safety labs (Haematology, Chemistry, Urinalysis) ^C	X			X								X								X	X
Methaemoglobin (SpMet) ^N	X			X								X								X	
Coagulation Blood Screen	X																				
HIV Test and CD4 Count	X																				
Urine Drug Screen	X																				
β-HCG Serum Pregnancy Test ^O	X																				X

EBA: Early bactericidal activity, EWD: Early withdrawal, FEV1: Forced Expiratory Volume in the first second, FU: Follow-up; IMP: Investigational Medicinal Product

- A: Follow-up visit: a window of ± 3 days allowed.
- B: Physical examinations: Full will be complete at screening and targeted (symptom-directed) thereafter.
- C: Vital signs, safety laboratory: on days where there is IMP dosing, to be performed pre-dose.
- D: IMP administration: The HRZE is to be administered fasted (1 hour before, or 2 hours after food) with approximately 240 mL of water. For study purpose this food should be breakfast. Patient identification is part of the IMP administration process. Experimental arms will not receive IMP on Day 15, only control arm will receive HRZE.
- E: Concomitant Medication: collected from 14 days prior to first dose of IMP.
- F: Adverse Events: Collected from first dose of IMP to Follow-Up visit.
- G: Eligibility Assessment: Continuous from screening to just prior to first IMP dose.
- H: EBA unit inpatient: admission, anytime from initial screening to day -2, whichever is in the participant's best interest.
- I: EBA unit inpatient: discharge.
- J: Randomisation: May occur any time after eligibility has been confirmed to just prior to first IMP dose.
- K: Spot or Overnight Sputum: A screening and the last positive sputum sample (if >7 days after treatment start) on *M.tb* culture will be retained by the mycobacteriology laboratory for possible future testing. These samples contain the mycobacterium genetic material only, no participant genetic material is retained.
- L: Spot or Overnight Sputum: For eligibility assessments.
- M: Overnight sputum: Collection will start in the afternoons at approximately 15h00 and continue for 16 hours ± 1 hour overnight. The 16-hour sputum sampling for each of the sampling days must be finished prior to the administration of the next morning's IMP. Collection will be paused for 1 hour after any RESP301 dose that overlaps with the overnight sample collection window where applicable. If sputum collection is paused, participants to drink a cup of water before restarting (section 5.3.2).
- N: Methaemoglobin: Screening single measurement. Days 1, 8 and 14: continuous measurement for an hour ± 10 mins from start of treatment on the first dose of that day only.
- O: β -HCG Serum Pregnancy Test: All female participants (section 4.3.4).

2. Introduction

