2.2.2.5. Pharmacokinetics and Product Metabolism in Animals

The pharmacokinetic (PK) profile of sodium nitrite is based upon data from the literature.

Absorption

(Tepper J, 2014) conducted a study in the Sprague Dawley rat whereby nebulised sodium nitrite was administered by inhalation (for up to 120 minutes) at 10, 30 and 75 (female) / 90 (male) mg/kg/day for 26 weeks. Plasma nitrite Time at which C_{max} is observed (T_{max}) was observed immediately after the end of inhalation, and for the nitrate metabolite this was delayed until approximately 1-hour post-dose. Pre-dose plasma concentrations of nitrite were generally below the lower limit of quantitation of the assay in all animals on Day 1 and in vehicle-treated animals throughout the study.

Toxicokinetic assessments were carried out on study days 1, 28, 85, and 176 and no significant differences were observed in maximum observed plasma concentration (C_{max}) and area under the plasma concentration time curve (AUC) values for nitrite spanning the multiple assessments (see reference for details), which suggests that the reported values were at steady state. Plasma concentrations of nitrite decreased rapidly with a terminal half-life between 0.3 and 1.6 hours at steady state, while the half-life of the nitrate metabolite was consistently longer (between 1.4 and 11.8 hours). Similarly, C_{max} and AUC values of the nitrate metabolite were also lower in males. At 1-hour post-dose, increases in C_{max} and AUC were generally proportional to dose for both nitrite and nitrate. No accumulation of nitrite was observed, but slight accumulation of the nitrate metabolite was observed at the end of the 26-week study. Generally, C_{max} and AUC for plasma nitrite were lower in males than in females even though males received 90 mg/kg/day while females received 75 mg/kg/day. In addition, methaemoglobin levels were lower in male rats. The mechanistic basis for these possible sex differences is currently unknown.

Table 7: Mean steady state plasma nitrite toxicokinetic parameter values on Day 26 following a 2-hour inhalation administration of sodium nitrite to rats for 26 consecutive weeks.

Dose, mg/kg/d	Sex ^a	$t_{1/2}, h$	T_{max}, h	$C_{max}, \text{mg/mL}$	$AUC_{0-24\text{ h}}, \text{h}\text{-mg/mL}$
10	F	0.3	2	1.23	1.95
	M	MS	2	1.14	MS
30	F	1.6	2	4.32	12.4
	M	0.3	2	3.22	4.96
75	F	0.9	2.2	14.3	38.7
90	M	0.6	2	17.4	34

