2.2.3.2. Inhaled Sodium Nitrite Published Literature

Inhaled sodium nitrite, formulated similarly to RESP301, has been assessed during inhalation studies in man and was well tolerated based on clinical studies obtained from published literature. (Rix PJ, 2015) (Borlaug BA, 2016) (Parakaw T, 2017). Key points are noted in Table 10 with more detail in the IB and references.

To support its use, safety reviews for both sodium nitrite and nitric oxide by the inhaled and/or oral route have been performed by regulatory agencies from the chemical, occupational and food safety industries e.g., ECHA, EFSA and NIOSH.

Table 10: Key Points* of Inhaled Nebulised Sodium Nitrite Clinical Data from Literature

Summary	Relevant Results	Reference
The pharmacokinetics, pharmacodynamics, and tolerability of nebulized sodium nitrite (AIR001) following single and repeated inhalation were assessed in three individual studies, in which a total of 82 healthy male and female subjects were treated.	Pulmonary absorption of nitrite was rapid and complete, and plasma exposure dose was proportional through the MTD dosage level of 90 mg, without accumulation following repeated inhalation. At higher dosage levels, DLTs were orthostasis (observed at 120 mg) and hypotension with tachycardia (at 176 mg), but venous methaemoglobin did not exceed 3.0 % at any time in any subject. Neither the tolerability nor pharmacokinetics of nitrite was impacted by conditions of mild hypoxia, or co-administration with sildenafil.	(Rix PJ, 2015)
Double-blind, randomized, placebo-controlled, parallel-group study designed to study the effects of nebulised inhaled sodium nitrite on cardiovascular haemodynamics at rest and during exercise in subjects with heart failure with preserved ejection fraction.	The inhaled nitrite was well tolerated. No subject developed hypotension, cough, and bronchospasm or reported headache or other adverse effects after inhalation of nitrite. No subject developed clinically meaningful methaemoglobinaemia. Nitrite (NO ₂ ⁻) levels increased to 11.1±4.9 µmol/L in subjects receiving active drug (p<0.0001 vs baseline). The calculated half-life of nitrite in this study was 0.72±0.74 hours.	(Borlaug BA, 2016)

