5.3.3. Participant Compliance

The IMP will be administered and compliance checked by the investigator/designated site personnel. This process will be detailed in the Pharmacy Manual. Where applicable the following checks will occur:

RESP301 nebulisation:

- the participant identity matches the dispensed vials
- the number of RESP301 vials (A and B) before and after mixing and nebulisation
- the date and time of preparation of the nebuliser solution (start and stop)
- the date and time of inhalation of the nebulisation solution (start and stop)
- confirmation the nebuliser is empty/minimal solution remains when nebulisation is complete.
- The investigators or appropriately trained delegated study personnel will remain with the participant whilst they are being nebulised to observe correct administration and monitor SpMet.

HRZE tablets:

- Participants will be checked for IMP compliance by the investigators or study personnel via the hand-and-mouth procedure. Both the hand and mouth of the participant will be checked to ensure that the participant has swallowed the IMP.

This information will be recorded in the participant's source documents and eCRF where required. All packaging will be checked to ensure complete administration.

Table 17 contains guidelines on how to manage HRZE dosing for a participant experiencing vomiting.

[REDACTED]	[REDACTED]
[REDACTED]	[REDACTED]

Please consult the study medical monitor for guidance, caution should be given when considered repeat dosing. This is to be documented in source and in the eCRF.

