6.3. Safety and Tolerability Assessments

The safety and tolerability assessments (Table 20) will be performed at the time points described in the study flow chart.

[REDACTED]	[REDACTED]
	[REDACTED] [REDACTED] [REDACTED] [REDACTED] [REDACTED] [REDACTED] [REDACTED]
[REDACTED] [REDACTED] [REDACTED]	[REDACTED] [REDACTED]
[REDACTED]	[REDACTED]

7. Adverse Events

The investigators are responsible for eliciting adverse events by observing the participant and recording all adverse events observed or reported by the participant during the study.

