| Count                             | X               |         |         |           |        |        |        |        |        |         |         |         |          |          |          |          |          |          |
|                                   | X               |         |         |           |        |        |        |        |        |         |         |         |          |          |          |          |          |          |
| nancy Test L                      | X               |         |         |           |        |        |        |        |        |         |         |         |          |          |          |          |          |          |
|                                   | X               |         |         |           |        |        |        |        |        |         |         |         |          |          |          |          |          |          |

EBA: Early bactericidal activity, EWD: Early withdrawal, FEV1: Forced Expiratory Volume in the first second, FU: Follow-up; IMP: Investigational Medicinal Product

A: Physical examinations: Will be complete at screening and targeted (symptom-directed) thereafter.

B: Vital signs, safety laboratory: on days where there is Investigational Medicinal Product (IMP) dosing, to be performed pre-dose.

C: IMP administration: The HRZE is to be administered fasted (1 hour before, or 2 hours after food) with approximately 240 mL of water. For study purpose this food should be breakfast.

D: Concomitant Medication: collected from 14 days prior to first dose of IMP.

E: Adverse Events: Collected from first dose of IMP to Follow-Up visit.

F: Eligibility Assessment: Continuous from screening to just prior to first IMP dose.

G: EBA unit inpatient: admission, anytime from initial screening to day -2, whichever is in the participant's best interest.

H: Randomisation: May occur any time after eligibility has been confirmed to just prior to first IMP dose.

I: Overnight sputum: Collection will start in the afternoons at approximately 15h00 and

CONFIDENTIAL

11 of 67

Version 1.2

RESP30X-EBA: Statistical Analysis Plan

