##### Vital signs

Vital signs are recorded at each visit. The change from the baseline will be calculated. The data will be summarized by treatment and time of collection.

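### Dosing-day vital signs are scheduled pre-dose only, so their summary can show sustained shifts but not transient blood-pressure or heart-rate changes after inhalation

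*Protocol*

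**What the plan says.** Protocol 1.3 (Study Flow Chart) schedules vital signs at every visit. Note C fixes the timing: "Vital signs, safety laboratory: on days where there is IMP dosing, to be performed pre-dose". SAP 4.7, Table 5, note B has the same rule: "Vital signs, safety laboratory: on days where there is Investigational Medicinal Product (IMP) dosing, to be performed pre-dose". Protocol 6.3 states that the safety assessments "will be performed at the time points described in the study flow chart", so on the readable text the flow chart governs. The detail in Table 20 is redacted.

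Vital signs are a listed variable for the secondary safety objective (protocol 1.2). SAP 10.2.3 says: "Vital signs are recorded at each visit. The change from the baseline will be calculated". SAP 10.1 takes the first pre-treatment observation as baseline. Protocol 2.5 names vital signs among the measures meant to give early detection of treatment-attributable events.

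The one measurement scheduled around a dose is methaemoglobin saturation (SpMet): flow-chart note N asks for continuous recording for about an hour from the start of the first dose on Days 1, 8 and 14. Under protocol 5.3.3, staff "will remain with the participant whilst they are being nebulised to observe correct administration and monitor SpMet".

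**The concern.** The protocol's own background describes an agent whose blood-pressure effect would be expected soon after inhalation. Table 6 says nitrites lower blood pressure by vasodilation and reports a compensatory heart-rate rise in the dog. Table 10 reports, for nebulised sodium nitrite in healthy volunteers, that "DLTs were orthostasis (observed at 120 mg) and hypotension with tachycardia (at 176 mg"; in those same studies venous methaemoglobin never exceeded 3.0%. So the human dose-limiting effects cited are haemodynamic, while the only scheduled peri-dose measurement is methaemoglobin. Protocol 2.2.2.5 puts peak plasma nitrite in rats at the end of inhalation, and Table 10 reports no accumulation in humans on repeated inhalation.

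A reading before the morning dose is then a trough reading, and change from baseline compares one nearly nitrite-free value with another. The risk is in interpretation: unremarkable tables could be taken as evidence that RESP301 has no haemodynamic effect, or that the once-, twice- and three-times-daily schedules do not differ, when the acute effect was not measured.

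**Working it through.** The plan gives no figure to reproduce. The check asks how much nitrite from the previous dose is left when the scheduled reading is taken.

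**Inputs**
- Human half-life (protocol 2.2.3.2, Table 10): "The calculated half-life of nitrite in this study was 0.72±0.74 hours". Mean 0.72 h; mean plus one SD = 0.72 + 0.74 = 1.46 h.
- Rat cross-check (protocol 2.2.2.5): "Plasma concentrations of nitrite decreased rapidly with a terminal half-life between 0.3 and 1.6 hours at steady state". The upper value, 1.6 h, is used.
- Time since the previous dose: an assumption. Protocol 5.3.2 puts the first daily dose in the morning, but the three-times-daily spacing is redacted. The overnight gap is taken as 8 to 12 h, with 24 h for once daily. Note C does not say which dose it means, so 4 h and 6 h are shown for a reading before a later same-day dose.

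**Formula** (first-order decay): fraction of peak remaining = 2^(−gap / half-life).

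Example: 8 / 0.72 = 11.1 half-lives, and 2^(−11.1) ≈ 0.045%.

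| Hours since last dose | Half-life 0.72 h | 1.46 h | 1.6 h |
|---|---|---|---|
| 4 | 2.1% | 15.0% | 17.7% |
| 6 | 0.31% | 5.8% | 7.4% |
| 8 | 0.045% | 2.2% | 3.1% |
| 12 | 0.001% | 0.34% | 0.55% |
| 24 | about 0% | 0.001% | 0.003% |

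For comparison, one hour after peak the 0.72 h half-life leaves 2^(−1/0.72) = 38%.

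**Spread between participants.** The SD exceeds the mean, so half-lives are probably skewed. Assume a lognormal with mean 0.72 and SD 0.74: log-variance = ln(1 + (0.74/0.72)²) = 0.721, log-SD = 0.849, log-mean = ln 0.72 − 0.721/2 = −0.689. Keeping more than 5% of peak needs a half-life above gap × ln 2 / ln 20, which is 1.85 h at 8 h and 2.78 h at 12 h. The share of participants above these limits is about 6% and 2%.

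**Coverage.** Fourteen dosing days give 14, 28 and 42 planned RESP301 doses for the once-, twice- and three-times-daily schedules. On the readable text, none is followed by a vital-sign reading at a set time after inhalation.

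**The case against.** Several objections carry weight.

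- **Size of the expected effect.** The dose-limiting effects arose at 120 mg and 176 mg of another nebulised nitrite product, above its maximum tolerated dose of 90 mg. The study that supplied the half-life, in heart failure with preserved ejection fraction, reported no hypotension. Protocol 2.2.2.3 places the observed cardiovascular effects above the proposed clinical doses and calls the potential low. The RESP301 nitrite content is redacted, so no effect size can be predicted. All of this stands: the point concerns what the data can show and does not claim a hazard.
- **Other safety capture.** Participants are inpatients, staff watch each nebulisation, and adverse events are collected throughout. The interim safety criteria in SAP 9 use adverse-event grades, not vital-sign summaries. This also stands. It leaves asymptomatic change, which cannot become an adverse event unless someone measures it.
- **Redaction.** Table 20 may add post-dose readings. Protocol 6.3 makes that less likely but does not exclude it, and such readings might supplement note C without contradicting it.
- **Concentration is not effect.** The documents give no duration for the haemodynamic effect, so plasma half-life is only a proxy.

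A reader might infer that the tables will be flat whatever the drug does. The documents do not support that: pre-dose readings on Days 2 to 14 can show a sustained or cumulative shift.

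**Conclusion.** The point holds in a limited form. Every scheduled dosing-day vital-sign reading is pre-dose, so the planned summary can show sustained shifts but not transient post-inhalation changes in blood pressure or heart rate. After an assumed 8 to 12 h overnight gap, about 0.05% to 0.001% of peak nitrite remains at the mean half-life, and 2.2% to 0.3% at mean plus one SD. If 'pre-dose' could mean before a later dose about 4 h after the last one, 2% to 15% would remain and the conclusion is weaker.

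This rests on first-order decay, the assumed gap, the cited half-life applying to RESP301, and Table 20 adding no readings. It does not follow that the trial has no haemodynamic safety monitoring or that participants are at undue risk. The primary endpoint is unaffected. This is a worthwhile, inexpensive improvement to one descriptive part of the secondary safety endpoint.

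**What to change.** **Protocol note C and SAP note B.** Keep the safety laboratory samples and the existing vital-sign reading pre-dose, and say which dose is meant. Add one blood-pressure and heart-rate reading on Days 1, 8 and 14 at a fixed time relative to the end of inhalation, for example immediately after it, within the SpMet hour. Nebulisation time is redacted and the hour runs from the start of treatment, so the sponsor should confirm that the chosen time falls inside it. If Table 20 already lists post-dose readings, reconcile it with note C.

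**SAP 10.2.3.** Summarise post-dose minus same-day pre-dose change by arm, alongside change from baseline. Present Day 1 separately, because protocol 5.3.2 has half doses and a suggested short-acting beta agonist that day; the latter could itself alter heart rate. State that the new readings cover the first daily dose only, so they say little about second or third doses or differences between schedules. Label the existing vital-sign tables as pre-dose values.

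**Cost.** A few minutes per participant on three days, one extra eCRF time point and one extra summary. Participants are already inpatients and monitored in that hour, so no new visit is needed.
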